### 7.1.1. Sensitivity Analysis

Sensitivity analysis will be conducted to evaluate the sensitivity to the estimated treatment effect by the assumption of lumasiran reaching steady state of the treatment effect at month 3 and maintained through month 6.

- Sensitivity analysis 1 estimates the treatment effect of the primary endpoint without assuming equal treatment effect from month 3 through month 6. The analysis adds the interaction of visit and treatment to the primary MMRM model, when month 3 through month 6 data are used.
- Sensitivity analysis 2, similar to sensitivity analysis 1, estimates the treatment effect of the primary endpoint without assuming equal treatment effect from month 3 through month 6, but including all post-baseline data (including percent change from baseline at months 1 and 2)).

**Table 1:** Analyses of the Primary Endpoint

Analysis	Analysis Set	Statistical model	Data 
Primary analysis	Full Analysis Set	MMRM (subject, baseline, treatment, visit)	M3, M4, M5, M6
Sensitivity Analysis 1	Full Analysis Set	MMRM (subject, baseline, treatment, visit, treatment*visit)	M3, M4, M5, M6
Sensitivity Analysis 2	Full Analysis Set	MMRM (subject, baseline, treatment, visit, treatment*visit)	M1, M2, M3, M4, M5, M6

<sup>1Percent change from baseline in 24-hour urinary oxalate corrected for BSA at each month (M) to be used in the model.

# 7.2. Secondary Endpoints

For secondary endpoints assessed to Month 6, the analysis will compare randomized arms (lumasiran vs. placebo) using the Full Analysis Set. During the Double-Blind Period, data will be collected during Screening, Day 1 and Months 1, 2, 3, 4, 5 and 6 with the exception of eGFR which is also collected at Week 2. To control for type I error, the primary and selected secondary endpoints will be tested in a hierarchical order as described in Section 5.6.

Absolute change from baseline in 24-hour urinary oxalate corrected for BSA will be analyzed using an MMRM model as specified for the primary endpoint. The percent change in 24-hour urinary oxalate: creatinine ratio, the percent change and the absolute change in plasma oxalate from baseline to Month 6 will also be analyzed using a similar MMRM model to the primary endpoint with the exception being that the baseline variable will be the baseline value of the corresponding endpoint.

For the two plasma oxalate related endpoints, a separate enriched analysis set of patients (i.e., Plasma Oxalate Analysis set) will be used. The plasma oxalate analysis set is defined as those patients who received any amount of study drug and have a baseline plasma oxalate level  $\geq$  1.5\*LLOQ. The LLOQ of the plasma oxalate assay is 5.55 µmol/L. Because it is not

possible to quantify plasma oxalate levels below LLOQ using the assay, patients with baseline plasma oxalate levels near the LLOQ (i.e. <1.5\*LLOQ) are excluded from the analysis to ensure that meaningful reductions in plasma oxalate can be evaluated for the study population.

For binary endpoints, i.e., the proportion of patients with 24-hour urinary oxalate  $\leq$ 1.5 ULN and  $\leq$  ULN at Month 6 the number and associated percent of patients who met each threshold at Month 6 will be presented by treatment arm. Refer to Appendix A for the value of ULN. Binary endpoints will be analyzed using a Cochran-Mantel-Haenszel (CMH) test stratified by baseline urinary oxalate ( $\leq$ 1.70 mmol/24hr/1.73m² vs. >1.70 mmol/24hr/1.73m²). The odds ratio with the corresponding 95% confidence interval and associated p-value will be presented. In addition, the differences in proportion of responders and corresponding 95% confidence interval using the Newcombe method based on the Wilson score will also be presented.

For continuous endpoints (including eGFR), descriptive statistics will be generated by treatment arm. LS Mean (+/- standard error) by treatment arm will be plotted for continuous PD endpoints. Spaghetti plots will also be generated for all continuous endpoints.

Table 2: Analysis of Secondary Endpoints to Month 6^

Endpoints	Statistical Method	Analysis Population
Absolute change in 24-hour urinary oxalate to Month 6	MMRM	Full Analysis Set
Percent change in 24-hour urinary oxalate:creatinine ratio to Month 6	MMRM	Full Analysis Set
Percent change in plasma oxalate from baseline to Month 6	MMRM	Plasma Oxalate Analysis Set
Proportion of Patients with 24-hour urinary oxalate ≤1.5xULN at Month 6	СМН	Full Analysis Set
Proportion of Patients with 24-hour urinary oxalate ≤ULN at Month 6	СМН	Full Analysis Set
Absolute change in plasma oxalate from baseline to Month 6	MMRM	Plasma Oxalate Analysis Set

^eGFR will be summarized descriptively (i.e. no formal testing) because this endpoint is not expected to change during the 6 months.

The following secondary endpoints which are assessed beyond Month 6 will be summarized to demonstrate long-term durability of lumasiran using the All Lumasiran Treated Set.

Descriptive statistics of percent change in 24-hour urinary oxalate at and after 6 months of lumasiran will be presented by treatment sequence (lumasiran/lumasiran, placebo/lumasiran) and the all treated arm (pooling treatment arms). A Wilcoxon-signed rank test (2-sided) will be conducted to test the null hypothesis of no change from baseline at selected timepoints (Months 6, 12, 18, 30, 36, 42 and 54). Additionally, the mean percent change from baseline with associated 95% (CIs) confidence intervals at each selected timepoint will also be presented. Supportive figures of mean (+/-standard error) percent change will be generated.

Descriptive statistics of percent change in 24-hour urinary oxalate will also be generated at visits during the entire study using the FAS set. Supportive figure of mean (+/- standard error) percent change will also be generated. An analysis of the percentage of time that 24-hour urinary oxalate level is at or below the near-normalization threshold will be summarized. A patient is considered to have met the threshold if the 24-hour urinary oxalate level is  $\leq 1.5 \text{xULN}$  at a post-baseline visit.

For each patient, the percentage of time that 24-hour urinary oxalate level is at or below the near normalization threshold (ie,  $\leq 1.5 \text{xULN}$ ) will be calculated as follows:

$$\frac{cumulative\ months\ at\ or\ below\ near\ normalization\ threshold}{cumulative\ months\ of\ valid\ assessments}\times 100$$

where cumulative months at or below the near normalization will be defined as the summation across all intervals that met the threshold and cumulative months of valid assessments will be defined as the summation across all valid post-baseline collections.

Given that the sample collection varies during the study (e.g. monthly up until M9, every 3 months until M24, every 6 months until Month 60), the calculation will take into account the following considerations:

- Time will be restricted to a maximum of 36 months on lumasiran (that is, up to protocol defined month 36 visit for lumasiran/lumasiran arm or up to protocol defined month 42 visit for placebo/lumasiran arm) or premature treatment discontinuation, whichever occurs first.
- A linear interpolation method will be used for to determine the bookend dates at which the patient crossed into the threshold and crossed out of the threshold.

Descriptive statistics of percentage of time at or below the threshold (among the subset of patients who had at least one post-baseline value which met threshold) will be presented for each treatment sequence arm and the all treated arm. In addition, the number of patients and associated percentage of patients in each category (e.g. <25%,  $\ge25\%$  to <50%,  $\ge50\%$  to <75%,  $\ge75\%$  to 100%) will also be presented.

Descriptive statistics of eGFR at and after 6 months of lumasiran will be presented. Shift tables of eGFR categories from baseline to post-baseline visits and an overall worst post-baseline will also be generated.

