3.5. Method of Assigning Patients to Treatment Groups

Using the Interactive Response System (IRS), patients will be randomized 2:1 to the lumasiran or placebo arm. Randomization will be stratified by mean baseline urinary oxalate level (>1.70 mmol/24h/1.73m² versus ≤ 1.70 mmol/24h/1.73m²). The mean urinary oxalate level for stratification will be calculated using the values obtained from the first 2 valid baseline 24-hour urine collections.

Each patient will be uniquely identified in the study by a combination of the site number and patient identification number. Upon signing the informed consent form (ICF), the patient will be assigned a patient identification number by the IRS. The Investigator or his/her designee will contact the IRS to randomize the patient after confirming that the patient fulfills all the inclusion criteria and none of the exclusion criteria.

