7.1. Determination of Sample Size

The planned enrollment for the study is 30 patients.

Patients will be randomized 2:1 to receive lumasiran or placebo, respectively. Assuming the mean percent reduction from baseline to Month 6 in 24-hour urinary oxalate corrected for body surface area (BSA) is 17% in the placebo arm and the standard deviation in both arms is 25%, 24 patients will provide 90% power to detect a treatment difference of 37% at a 2-sided 5% significance level (ie, 54% reduction in the lumasiran arm). To account for potential drop-outs, 30 patients are planned to be enrolled in the study.

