### 5.5. Randomization Stratification Factors

The mean 24-hour urinary oxalate excretion ( $\leq$ 1.70 mmol/24h/1.73m^2 or >1.70 mmol/24h/1.73m^2) from the first 2 valid 24-hour urine collections during screening will be the stratification factor. The stratification factor will be recorded in both the IRS (Interactive Response System) and the clinical database.

The central laboratory for the 24-hour urinary oxa	alate measurements used for randomization
during screening was transitioned from	(i.e., Clinical Assay) to
(i.e., Validated PD assay). As a result, the first 5 s	
on the Clinical Assay	and the remaining patients were stratified
using the results based on the Validated PD Assay	y

The planned statistical methods will adjust for baseline 24-hour urinary oxalate (refer to Section 5.4 and Section 7.1) and may not match the stratification factors as recorded in IRS. Any discrepancies will be summarized.

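### Three of the six hierarchically tested secondary endpoints leave out baseline urinary oxalate, the only randomisation stratifier, an exception SAP 5.5 does not mention; power may be lost if it is prognostic

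*SAP*

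**What the plan says.** Protocol 3.5 names one stratification factor: "Randomization will be stratified by mean baseline urinary oxalate level", cut at 1.70 mmol/24h/1.73m². By the same section, "patients will be randomized 2:1 to the lumasiran or placebo arm". The primary MMRM (SAP 7.1) carries baseline 24-hour urinary oxalate as a continuous covariate.

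The secondary analyses, in the order of SAP 5.6 and with the methods of SAP 7.2, are:

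| Step | Endpoint | Analysis set | Baseline urinary oxalate in the analysis? |
|---|---|---|---|
| 1 | Absolute change, urinary oxalate | FAS | Yes (primary model) |
| 2 | % change, oxalate:creatinine ratio | FAS | No, own baseline instead |
| 3 | % change, plasma oxalate | Plasma Oxalate Analysis Set | No, own baseline instead |
| 4 | At or below 1.5×ULN | FAS | Yes (stratified CMH) |
| 5 | At or below ULN | FAS | Yes (stratified CMH) |
| 6 | Absolute change, plasma oxalate | Plasma Oxalate Analysis Set | No, own baseline instead |

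For steps 2, 3 and 6 the model resembles the primary one, "with the exception being that the baseline variable will be the baseline value of the corresponding endpoint". This is a replacement, not an addition.

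SAP 5.5 says: "The planned statistical methods will adjust for baseline 24-hour urinary oxalate". The sentence then refers the reader to Section "5.4 and Section 7.1) and may not match the stratification factors as recorded in IRS". Protocol 7.2.5.2 asks only for an MMRM similar to the primary one. The list of changes in SAP 8 neither mentions nor justifies the replacement.

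**The concern.** Stratified randomisation balances the arms on urinary oxalate, so the treatment contrast varies less from trial to trial on that account. A model that omits the factor leaves its contribution in the residual variance. If the factor predicts the outcome beyond what the model already holds, the standard error is too large and the test rejects too rarely.

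Position in the hierarchy is what makes this worth raising. Steps 2 and 3 stand before both responder endpoints, and a miss at either ends formal inference for everything below it. Step 3 also runs on a restricted set (baseline plasma oxalate at least 1.5 × 5.55 = 8.325 µmol/L) whose size is not stated. No power is given for any secondary endpoint. In addition, someone programming from 5.5 and someone programming from 7.2 could build different models for three alpha-controlled tests.

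**Working it through.** **1. The plan's own figure.** Protocol 7.1: "24 patients will provide 90% power to detect a treatment difference of 37% at a 2-sided 5% significance level". The assumed mean reduction is "17% in the placebo arm and the standard deviation in both arms is 25"%. With 2:1 allocation, 24 patients are 16 and 8. The noncentrality is 37 / (25 × √(1/16 + 1/8)) = 37 / 10.83 = 3.42 on 22 df, which gives 90.4% power and reproduces the stated 90%. Protocol 7.1 adds: "To account for potential drop-outs, 30 patients are planned to be enrolled in the study"; the implied allowance is (30 − 24)/30 = 20%. All this concerns the primary endpoint, which the point does not touch. It does supply the only documented planning effect: 37/25 = 1.48 SD.

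**2. Size of the conservatism in principle.** Let f be the share of variance, after the own baseline, that the stratum explains. With exact balance, and a stratum unrelated to the own baseline, the null rejection rate is about 2[1 − Φ(1.96/√(1 − f))]:

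- f = 0.10: 1.96/0.949 = 2.07, rate 3.9%
- f = 0.20: 1.96/0.894 = 2.19, rate 2.8%
- f = 0.30: 1.96/0.837 = 2.34, rate 1.9%

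Imperfect balance in small strata and overlap with the own baseline pull these back towards 5%.

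**3. Simulation with a continuous predictor.** Thirty patients, 2:1 permuted blocks of three within two strata cut at the median, one averaged outcome per patient, and ANCOVA standing in for the MMRM. Let U be standardised baseline urinary oxalate and B the own baseline, with corr(U, B) = r. Let U′ = (U − rB)/√(1 − r²). The outcome is Y = δT + 0.5B + ρU′ + √(1 − ρ²)e, so ρ is the partial correlation and ρ² the share explained. The values of r, ρ and δ are assumptions: r = 0.3 for a plasma-like and 0.8 for a ratio-like endpoint. There were 8,000 runs per setting (6,000 for the subset). Entries are percentages; power is at δ = 1.2 residual SD.

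| Setting | ρ (ρ²) | Type I, own baseline only | Type I, plus U | Power, own baseline only | Power, plus U | Power, plus stratum |
|---|---|---|---|---|---|---|
| N=30, r=0.3 | 0 (0%) | 5.2 | 5.2 | 83.3 | 82.8 | 83.2 |
| | 0.3 (9%) | 4.3 | 5.0 | 83.2 | 85.3 | 84.3 |
| | 0.5 (25%) | 3.5 | 5.1 | 84.5 | 91.6 | 88.3 |
| | 0.7 (49%) | 2.4 | 4.9 | 86.3 | 98.1 | 93.6 |
| N=30, r=0.8 | 0 (0%) | 4.9 | 5.0 | 84.0 | 82.9 | 83.3 |
| | 0.3 (9%) | 4.9 | 5.3 | 83.9 | 85.6 | 84.1 |
| | 0.5 (25%) | 4.5 | 5.4 | 84.7 | 91.9 | 86.9 |
| | 0.7 (49%) | 3.7 | 4.9 | 85.4 | 98.2 | 90.1 |
| 60% subset chosen on B, r=0.3 | 0 (0%) | 5.0 | 5.2 | 57.4 | 54.7 | 55.1 |
| | 0.3 (9%) | 5.1 | 5.2 | 56.6 | 58.7 | 57.7 |
| | 0.5 (25%) | 4.8 | 5.6 | 56.9 | 66.4 | 62.0 |
| | 0.7 (49%) | 3.6 | 5.2 | 57.8 | 81.7 | 70.7 |

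Monte Carlo error is about 0.25–0.3 points on type I error and at most 0.65 on power.

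**4. Simulation with the share attributed to the stratum itself.** At N=30 with 10 / 20 / 30% explained, type I error under the planned model is about 3.8–4.3 / 3.4–4.3 / 2.4–3.8%. Adding the stratum gains about 2–9 points of power at an assumed 1.1 SD effect, and about 2–13 points in a 20-patient plasma subset. At 1.48 SD, N=30 and own-baseline correlation 0.5, power moves from 95.5 to 96.3%, 95.9 to 98.1% and 96.5 to 98.9%: gains of 0.8, 2.2 and 2.4 points.

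**The case against.** The case for leaving the plan alone is substantial. Adjusting each endpoint for its own baseline is a defensible, prespecified choice, and the protocol requires only a similar model. Any error runs against the sponsor. The oxalate:creatinine ratio comes from the same 24-hour collections as urinary oxalate (Protocol 6.3.1.2), so its own baseline plausibly carries much of the stratifier; at r = 0.8 type I error is 3.7–4.9%. Selecting the plasma set on baseline plasma oxalate weakens the stratified balance, so conservatism is also mild there (3.6–5.1% in the 60% subset). All of this stands, and it limits the size of the point.

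Three stronger readings are tempting, and the documents support none of them.

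- A reader might infer that the three tests are in fact conservative. That needs urinary oxalate to predict each outcome beyond its own baseline, and neither document reports that relation. With none, type I error stays at about 5%.
- A reader might infer that SAP 5.5 and 7.2 contradict each other. The 5.5 sentence is worded without limit, but it points to 5.4 and 7.1, and its purpose is to explain why the analysis baseline may differ from the stratum held in the IRS. Section 7.2 then states a specific exception. What is missing is any mention of that exception in 5.5.
- A reader might infer that the IRS stratum is the term that must be added. SAP 5.5 reports that the first five patients were stratified on a different assay, and the primary model uses the continuous validated-assay value.

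The objection does not explain why the stratifier is kept for the CMH tests but dropped, without comment, from the continuous models in the same hierarchy.

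**Conclusion.** The point holds in a conditional form. It is certain that steps 2, 3 and 6 omit the only stratifier while the primary analysis and steps 1, 4 and 5 keep it, and that 5.5 is silent on the exception. The consequence depends on a prognostic relation the documents do not give. If urinary oxalate explains 10–30% of the remaining variance and the effect is 1.1 SD, type I error is about 2.4–4.3% at N=30, and the loss is about 2–9 points of power, or about 2–13 points in a 20-patient plasma subset. At N=30 the loss shrinks to roughly 1–2.5 points if the effect is near the 1.48 SD planned for the primary endpoint; borrowing that figure for other endpoints is itself an assumption. The plasma subset size, the correlations and the block size are also assumed.

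A reader might suspect an inflated error rate or a biased estimate. Neither follows: the direction is conservative. This is a point of efficiency and clarity, and it matters chiefly because steps 2 and 3 gate the responder endpoints.

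**What to change.** In SAP 7.2, keep the endpoint's own baseline and add baseline 24-hour urinary oxalate as a fixed effect in the MMRMs for the oxalate:creatinine ratio and the two plasma oxalate endpoints. Either the continuous validated-assay value, which matches the primary model, or the randomised stratum is acceptable, provided that one is prespecified before unblinding. Reword 5.5 so that it agrees with 7.2. If the omission is intended, limit the 5.5 sentence to the analyses it covers and give the reason in 7.2.

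The cost is one term and one degree of freedom in each of three models. If urinary oxalate turns out not to be prognostic, that is about 1 point of power at N=30 and about 1–3 points in a small plasma set (57.4 to 54.7% in the 60% subset above).

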7.2.5.2. Secondary Endpoints

To control the overall type I error, these secondary endpoints will be tested in the following hierarchical order:

- Absolute change in 24-hour urinary oxalate corrected for BSA from baseline to Month 6
- Change in 24-hour urinary oxalate:creatinine ratio (value/ULN) from baseline to Month 6
- Proportion of patients with 24-hour urinary oxalate level at or below 1.5 x ULN at Month 6
- Proportion of patients with 24-hour urinary oxalate level at or below ULN at Month 6
- Percent change in plasma oxalate from baseline to Month 6
- Absolute change in plasma oxalate from baseline to Month 6

Continuous endpoints will be analyzed using an MMRM approach similar to the one described for the primary endpoint. Binary endpoints will be analyzed using the Cochran-Mantel-Haenszel test stratified by baseline urinary oxalate. The odds ratio and the differences in proportions with corresponding 95% confidence will also be summarized.

Secondary endpoints assessed beyond Month 6 will be summarized descriptively. Change in eGFR over time will also be summarized descriptively.

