### 3.1.2. Secondary Objectives

- To characterize the effect of lumasiran on absolute levels of urinary oxalate excretion, urinary oxalate: creatinine ratios, and plasma oxalate
- To evaluate the long-term effect of lumasiran
- To evaluate the effect of lumasiran on renal function

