### 3.2.2. Secondary Endpoints

- Absolute change in 24-hour urinary oxalate corrected for body surface area (BSA) from baseline to Month 6
- Percent change in 24-hour urinary oxalate: creatinine ratio from baseline to Month 6
- Percent change in plasma oxalate from baseline to Month 6
- Proportion of patients with 24-hour urinary oxalate level at or below 1.5xULN at Month 6
- Proportion of patients with 24-hour urinary oxalate level at or below ULN at Month 6
- Absolute change in plasma oxalate from baseline to Month 6
- Change in in estimated glomerular filtration rate (eGFR) from baseline to Month 6
- Change from baseline (percent and absolute) 24-hour urinary oxalate excretion, percentage of time that 24-hour urinary oxalate is ≤1.5 × ULN, 24-hour urinary oxalate: creatinine ratios and eGFR in the extension periods

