### **5.2.** General Methods

Continuous data will be described using descriptive statistics such as the number of observations (n), mean, standard deviation, standard error, median, quartiles, minimum, and maximum. For the summary statistics of all numerical variables unless otherwise specified, minimum and maximum will be displayed to the same level of precision as reported. Median and mean will be presented to the level of precision collected in database plus one additional decimal. Standard deviation and standard error will be presented to the level of precision collected in the database plus 2 additional decimals.

For assessments with repeated collections at a given study visit (e.g. ECG parameters, height for ages<18 years old), the mean will represent the value at the visit for all parameters except for 24-hour urine PD parameters. For 24-hour urine PD parameters, if there are any repeated collections at a visit, then the median will represent the value at that visit. For biomarker and/or lab data, if any value is recorded as <lower limit of quantification (LLOQ) then the assigned value used for calculations of summary statistics will be assigned a value of the LLOQ.

Categorical and ordinal data will be described using the patient count and percentages in each category. When count data are presented, the percentage will not be presented when the count is zero.

Tables and figures will primarily summarize data during the double-blind period and during lumasiran treatment. These time periods are defined directly below. In addition, there will be a subset of tables and figures for efficacy endpoints which will also summarize by protocol defined study visit across the entire study for patients in the FAS set.

**During the Double-Blind (DB) Period:** defined as the time period prior to the first study drug dose date/time in the extension period (e.g. date/time of lumasiran dose at month 6).

Tables and figures will be presented by treatment arm (lumasiran or placebo). For safety summaries (i.e. AEs, Labs, ECGs, VS, etc.), all assessments up to the date/time of the first dose in the extension period (i.e. date/time of lumasiran at month 6) or, for patients not dosed in the extension period, all assessments collected within 84 days of the last dose of study drug will be included. For efficacy summaries, all data up to and including the month 6 visit will be presented.

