Formal statistical hypothesis testing will be performed on the primary and secondary efficacy endpoints evaluated during the DB period (except eGFR as this endpoint is not expected to change within six months). Testing will be conducted at the nominal 2-sided 0.05 level of significance. Secondary endpoints will be tested in a prespecified hierarchy (Section 5.6). Summary statistics will be presented, as well as 2-sided 95% confidence intervals on selected parameters, as described in the sections below.

All data recorded on the CRF will be displayed in data listings.

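### Renal function is a secondary objective, but the SAP prespecifies no baseline-adjusted between-arm eGFR difference or confidence interval for the only controlled period

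*SAP*

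**What the plan says.** SAP 3.1.2 lists among the secondary objectives "To evaluate the effect of lumasiran on renal function", and SAP 3.2.2 lists as a secondary endpoint the change in "estimated glomerular filtration rate (eGFR) from baseline to Month 6". Change in eGFR during the extension periods is also a secondary endpoint.

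SAP 7.2 opens with a general rule: "For secondary endpoints assessed to Month 6, the analysis will compare randomized arms (lumasiran vs. placebo) using the Full Analysis Set". It then assigns an MMRM or a CMH test to each of the other Month 6 secondary endpoints. eGFR is not among them. Its analysis is: "For continuous endpoints (including eGFR), descriptive statistics will be generated by treatment arm", plus spaghetti plots. The Table 2 footnote gives the reason: "eGFR will be summarized descriptively (i.e. no formal testing) because this endpoint is not expected to change during the 6 months". SAP 5.2 says the same when it lists the endpoints to be tested: "except eGFR as this endpoint is not expected to change within six months". Protocol 7.2.5.2 agrees: "Change in eGFR over time will also be summarized descriptively".

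SAP 5.2 defines the descriptive set as "the number of observations (n), mean, standard deviation, standard error, median, quartiles, minimum, and maximum". It promises 95% confidence intervals only for selected parameters described in later sections, and no later section describes one for eGFR. SAP 7.7.2 (laboratory data) does not report eGFR and refers it to the efficacy section. Shift tables of eGFR category appear in SAP 7.2, in the text on long-term treatment.

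**The concern.** The general rule in SAP 7.2 promises a comparison of randomised arms, but eGFR is given no comparative method. This matters because the double-blind period cannot be repeated. From Month 6 every patient receives lumasiran (Protocol 3.1), so later eGFR summaries and shift tables have no concurrent control.

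The stated reason bears on testing, not on estimation. If no change is expected, a superiority test has little purpose, but an interval gains in value because it shows what decline the data still allow. Two arm means side by side, from about 20 and 10 patients, do not show that. They are also unadjusted. Randomisation is stratified only by urinary oxalate (Protocol 3.5), and entry requires only an eGFR of at least 30 mL/min/1.73m² (Protocol 4.2), so a chance imbalance in baseline eGFR is plausible at this size.

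At stake is whether the report says, in a form fixed beforehand, how large an eGFR loss the randomised data exclude.

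**Working it through.** **1. The plan's own figure.** The documents state no precision for eGFR. The only stated sample-size figure is for the primary endpoint (Protocol 7.1, SAP 5.1): 24 patients, 90% power, difference 37 points, SD 25, 2:1 allocation, two-sided 5%.

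- Placebo n = (1.960 + 1.282)² × 25² × (1 + 1/2) / 37² = 7.2, rounded up to 8. Lumasiran n = 16. Total 24, as stated.
- Power with a t-test at 16:8 is 90.4%.
- 24 / (1 − 0.20) = 30, so planned enrolment implies a 20% allowance for drop-out.

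The sample size is not in dispute. It supplies the two splits used below: 20:10 (all 30 contribute) and 16:8 (24 contribute).

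**2. Precision of a between-arm difference in eGFR change at one visit, unadjusted.**

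Half-width = t(0.975, n1 + n2 − 2) × SD × √(1/n1 + 1/n2)

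- 20:10: √(1/20 + 1/10) = 0.387; t with 28 df = 2.048; half-width = 0.793 × SD.
- 16:8: √(1/16 + 1/8) = 0.433; t with 22 df = 2.074; half-width = 0.898 × SD.

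The SDs below are assumptions, since the documents give none for eGFR change. Half-widths are in mL/min/1.73m².

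| Assumed SD | 20:10 | 16:8 |
|---|---|---|
| 8 | 6.3 | 7.2 |
| 10 | 7.9 | 9.0 |
| 12 | 9.5 | 10.8 |
| 15 | 11.9 | 13.5 |

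If the observed difference were zero, only losses larger than the half-width would be excluded.

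**3. What the planned tables already allow.** With an assumed SD of 10 and 20:10 patients, the arm-level standard errors would be 10/√20 = 2.24 and 10/√10 = 3.16. The standard error of the difference is √(2.24² + 3.16²) = 3.87, and 2.048 × 3.87 = 7.9, which matches the table. A reader given the change from baseline by arm can therefore derive an unadjusted interval. The baseline adjustment cannot be recovered from those summaries.

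**4. Comparison within the SAP.** For the uncontrolled extension data, SAP 7.2 plans 95% confidence intervals for the mean percent change in urinary oxalate at selected months. For eGFR in the randomised period it plans none.

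**The case against.** The strongest reply is that the choice is deliberate, explained and consistent. Protocol 7.2.5.2, SAP 5.2 and the Table 2 footnote agree, eGFR is outside the hierarchy, no planned inference is wrong, and nothing in the SAP announces a conclusion of no renal effect. All of that is true. It makes this an improvement to the plan rather than the correction of an error. It does not answer the point about estimation, because the reason given covers testing only.

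Three stronger readings are tempting, and the documents support none of them.

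- A reader might infer that the randomised data cannot show how large a loss is excluded. The planned n, mean and standard error by arm allow an unadjusted interval, as shown in the working. What is missing is an interval that is prespecified, baseline-adjusted and reported.
- A reader might infer that Month 6 eGFR is the only endpoint serving the renal objective. Change in eGFR in the extension periods is also a secondary endpoint, and spaghetti plots and shift tables will show individual declines. None of these is a controlled contrast.
- A reader might infer that averaging Months 3 to 6, as for the primary endpoint, would sharpen the estimate. SAP 7.1 justifies that window by the oxalate effect reaching steady state and by the variability of 24-hour urinary oxalate. Neither argument is made for eGFR. The gain also depends on an unknown between-visit correlation r: √((1 + 3r)/4) gives a 26% narrower interval at r = 0.4 and 4% narrower at r = 0.9.

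Two limits stand. The interval will be wide, so the practical gain is modest. A pooled difference also mixes two eGFR formulae, MDRD for adults and Schwartz for children (Protocol 6.3.2). Because the formula is set by age at screening, each patient's change stays within one formula, but the pooled estimate should carry that caveat.

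**Conclusion.** The point holds as a low-cost improvement. The SAP names a renal-function objective, has one controlled period in which to address it, and prespecifies no baseline-adjusted between-arm eGFR difference or interval for that period. The plan therefore does not report how large an eGFR loss the randomised data exclude.

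The size rests on the assumed SDs and on the two splits, before any gain from baseline adjustment. Over that range the data would exclude only losses beyond somewhere between 6.3 and 13.5 mL/min/1.73m² if the arms looked identical. Similar arm means could therefore coexist with a loss of several mL/min. The primary analysis, the sample size and type I error control are not affected.

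**What to change.** In SAP 7.2, add the lumasiran-minus-placebo LS mean difference in change in eGFR at Month 6, with its 95% CI, in the Full Analysis Set. Estimate it from an MMRM with baseline eGFR as covariate and treatment, visit and treatment-by-visit as fixed effects. This is the Sensitivity Analysis 1 form (SAP 7.1.1), fitted to the scheduled post-baseline eGFR visits: Week 2 and Months 1 to 6. An unstructured matrix for seven visits has 7 × 8 / 2 = 28 parameters, so the covariance fallback in SAP 7.1 should be carried over explicitly. Report no p-value, and keep the estimate outside the Section 5.6 hierarchy. Do not add a Months 3 to 6 average. Keep the descriptive tables and plots, and record the change in SAP Section 8.

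The cost is one more model run on data already scheduled. There is no added patient burden and no alpha is spent. The downside is a visibly wide interval that will exclude only fairly large losses. If the double-blind data have already been unblinded, the same estimate can be given but should be labelled post hoc.
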